Recently, impaired myocardial blood flow reserve, reduced myocardial energy utilization, and increased myocardial fibrosis have been postulated to play important pathophysiologic roles in HFpEF.⁵ We and others have demonstrated that HFrEF may be associated with altered myocardial energy utilization and “energy starvation.”⁶ However, there is limited data regarding “energy starvation” in HFpEF and the relationships between myocardial blood flow reserve, energy utilization, and fibrosis in HFpEF are largely unknown.⁷ Therefore, the purposes of this study are to use non-invasive cardiac imaging techniques to describe cardiac perfusion, energetics, and fibrosis, and their relationships, in order to better understand underlying mechanisms in HFpEF.

Specifically, we hypothesize that HFpEF is associated with reductions in myocardial blood flow reserve and energy utilization and increased myocardial fibrosis as compared to gender matched hypertensive and healthy controls. We will test our hypotheses by comparing measurements of myocardial blood flow reserve, energy utilization, and fibrosis between three subject groups (HFpEF vs hypertension vs healthy). Myocardial blood flow will be quantitated from ¹³N-Ammonia Positron Emission Tomography (PET) and gadolinium enhanced cardiac magnetic resonance imaging (cMRI) both at rest and stress following coronary vasodilation with regadenoson. Myocardial energy utilization will be quantified with ¹¹C-Acetate PET imaging and myocardial fibrosis will be assessed with gadolinium enhanced MRI. Echocardiography will be utilized to quantify diastolic function and myocardial strain.

It is anticipated that the results of this proposed study will provide a foundation that will inform future studies aimed at identifying novel preventive or therapeutic agents in HFpEF. In addition, the design of the study affords opportunities to compare myocardial perfusion between PET and cMRI across a spectrum of patient populations and obtain valuable normative perfusion data in an age group most likely to undergo stress testing. Importantly, the findings may also help establish a role for regadenoson stress myocardial perfusion imaging in the evaluation of coronary endothelial function and myocardial blood flow in hypertensive and HFpEF patients.

Specific Aims

Heart failure with preserved ejection fraction (HFpEF) is a major public health problem. HFpEF accounts for half of all new cases of heart failure (HF), is increasing in prevalence, and portends a poor prognosis. Unfortunately, medical therapies with proven mortality benefit in HFpEF are lacking. The absence of effective therapies is attributable in part to the poor understanding of the underlying mechanisms of HFpEF.

Coronary endothelial dysfunction and impaired myocardial blood flow reserve are postulated to be important mechanisms in HFpEF. The delivery of oxygen and fuel sources needed for myocardial performance is dependent upon myocardial blood flow. Impaired myocardial blood flow at stress can occur even in the absence of flow limiting epicardial coronary artery disease, may be a marker of coronary endothelial dysfunction, and is associated with adverse cardiovascular outcomes.⁸ However, coronary endothelial function and myocardial blood flow reserve have not been well described in HFpEF.

Experimental and clinical evidence suggests that myocardial oxidative metabolism is impaired in HF. Impaired oxidative metabolism has been associated with HF with *reduced* ejection fraction (HFrEF). However, few studies have investigated oxidative metabolism in HFpEF and in particular, whether differences in oxidative metabolism exist between hypertensive patients and those with HFpEF.

Myocardial fibrosis is regarded as an important mechanism for HFpEF. Increased extracellular fibrosis has been observed in animal models of hypertension, human left ventricular hypertrophy, and endomyocardial biopsies from patients with HFpEF. Hypertension is the major risk factor for HFpEF; however, it is unknown why some individuals with hypertension develop progressive myocardial fibrosis.

Experimental evidence suggests that impaired oxidative metabolism contributes to myocardial fibrosis. In animal models of hypertension, therapies targeting oxidative metabolism have been associated with decreased LV fibrosis. Consequently, understanding oxidative metabolism and myocardial fibrosis in HFpEF is of biologic importance and may have therapeutic implications.

In preliminary work, we have shown that we can quantitatively measure myocardial blood flow reserve, oxidative metabolism and myocardial fibrosis through non-invasive cardiac imaging. Myocardial blood flow reserve can be quantitatively measured with cardiac magnetic resonance imaging (cMRI) and positron emission tomography (PET). The mono-exponential

decay rate (K_{mono}) of ^{11}C -Acetate determined with PET is a validated measure of myocardial oxidative metabolism. Fibrotic myocardium can be quantified using cMRI T1 mapping.

We postulate that reduced myocardial blood flow reserve contributes to impaired oxidative metabolism and increased myocardial fibrosis in HFpEF. We propose to test the following primary hypotheses: 1) Compared to healthy and hypertensive individuals, subjects with HFpEF have reduced myocardial blood flow reserve, 2) Compared to healthy and hypertensive individuals, subjects with HFpEF have reduced oxidative metabolism; 3) Compared to healthy and hypertensive individuals, subjects with HFpEF have increased myocardial fibrosis, and 4) Myocardial blood flow reserve is positively correlated with oxidative metabolism and inversely correlated with myocardial fibrosis.

Aim 1. To compare myocardial blood flow reserve in individuals with HFpEF versus those with hypertension and healthy individuals. We will enroll 60 subjects (20 HFpEF, 20 hypertensive, and 20 healthy) who will undergo cMRI and ^{13}N -Ammonia PET to quantify myocardial blood flow at rest and during pharmacologic stress with regadenoson.

Aim 2. To compare myocardial oxidative metabolism in individuals with HFpEF versus those with hypertension and healthy individuals. Subjects enrolled in aim 1 will also undergo ^{11}C -Acetate PET imaging to quantify oxidative metabolism via the mono-exponential decay rate of ^{11}C -Acetate.

Aim 3. To compare myocardial fibrosis in individuals with HFpEF versus those with hypertension and healthy individuals. Subjects enrolled in aim 1 will also undergo cMRI with T1 mapping to quantify myocardial fibrosis.

Aim 4. To assess the relation between myocardial blood flow reserve, oxidative metabolism and fibrosis. The correlations between myocardial blood flow reserve, oxidative metabolism and fibrosis will be evaluated.

2. Study Design

2.2 Recruitment of Study Sample

2.2.1 Cohorts Defined

Heart Failure Preserved Ejection Fraction (n=20). HFpEF patients will be aged 50 years or older, have a physician confirmed diagnosis of HF, be symptomatic (New York Heart Association class II or III), with a LVEF $\geq 50\%$ within the prior 6 months, and no prior history of LVEF $< 50\%$. HFpEF subjects will have evidence of elevated LV filling pressures by ≥ 1 of the following within the last 6 months: invasive cardiac catheterization LV end diastolic pressure or pulmonary capillary wedge pressure > 12 mmHg, plasma B-type natriuretic peptide > 100 pg/ml, or echocardiographic $E/e' > 15$. HFpEF patients with known coronary artery disease (CAD) or angina) will be excluded to reduce potential confounding. Patients with significant valvular (\geq moderate stenosis or regurgitation), pericardial, or congenital heart disease, or symptoms due predominantly to right heart failure and pulmonary arterial hypertension will also be excluded, as will those with an estimated glomerular filtration rate (eGFR) < 45 ml/min/1.73m². HFpEF patients in acute decompensated heart failure requiring intravenous diuretics, hospitalization, or use of intravenous vasoactive medications will be eligible for screening, but must be compensated at the time of the protocol visit. HFpEF patients will be recruited through the Vanderbilt Heart and Vascular Institute HFpEF program.

Healthy (n=20): We will enroll volunteers matched on gender to the HFpEF group. Healthy subjects will be free of known cardiovascular disease (HF or cardiomyopathy, CAD, valvular heart disease, pericardial disease, arrhythmias, stroke, peripheral arterial disease), cardiovascular risk factors (hypertension, DM, tobacco use, dyslipidemia, family history of cardiovascular disease, CKD, autoimmune disorder), or use of medications for cardiovascular disease or its risk factors. In addition, healthy individuals must have normal cardiac structure and function, to be confirmed by conventional transthoracic echocardiography at the time of the screening visit. We will use the "Research Studies" email sent to accounts at Vanderbilt University Medical Center and the Research Study Volunteer Program, a registry that enables identification of healthy volunteers.

Hypertensive (n=20). We will recruit subjects matched on gender to the HFpEF group. Subjects in the hypertensive group will have a physician confirmed diagnosis of hypertension, but without known cardiovascular disease (as defined above). Hypertension will be defined as a physician confirmed diagnosis of hypertension, history of blood pressure $> 140/90$ mmHg and treatment with ≥ 1 anti-hypertensive medication. At the time of the protocol visit, the hypertensive subjects must have adequate blood pressure control, defined as $< 160/100$ mmHg. Hypertensive subjects with other cardiovascular risk factors (as previously defined) will be excluded to reduce confounding. In addition, hypertensive individuals must have preserved LVEF, defined as $\geq 50\%$. We will recruit hypertensive patients through several means, including the "Research Studies" email sent to accounts at Vanderbilt University Medical Center,

identification of patients from the Vanderbilt Heart and Vascular Institute clinics, and Vanderbilt general medicine and Hypertension clinics.

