2.2.2 Inclusion/Exclusion Criteria

Subject Selection: Regardless of study group, any potential subjects with contraindications to cardiac imaging or adverse reactions to echocardiographic contrast, ¹¹C Acetate, gadolinium, regadenoson or its reversal agent (aminophylline), or ¹³N-Ammonia will be excluded. Based upon the number of subjects needed for the study, we expect the number of subjects screened and eligible will exceed the number needed to enroll. An important aspect of the inclusion/exclusion criteria is the age requirement of ≥ 50 years old. The typical HFpEF patient is in the sixth decade of life or older,^{9, 10} and therefore, in order to capture a representative HFpEF population, we will specifically target this age range. Recruitment will be monitored on an ongoing basis by the PI. The investigators’ research group has substantial experience recruiting participants into clinical studies and trials using the mechanisms outlined above.

Table 2. Key Inclusion and Exclusion Criteria		
Study Group	Inclusion	Exclusion
All	
 Age ≥ 50 years Able to provide informed consent eGFR ≥ 45 ml/min/1.73m² 	
 Coronary artery disease Contraindication to cMRI (e.g. claustrophobia, metal) Weight > 350 lbs (PET & MRI limits) Inability to lie flat for imaging Pregnancy Anemia, Hgb < 10 Contraindication to regadenoson or aminophylline
Healthy	
 Normal cardiac structure & function BP < 140/90 mmHg 	
 Known cardiovascular disease (see text), risk factors (see text), or use of cardiac medications Diabetes Mellitus
Hypertensive	
 History of BP > 140/90 mmHg ≥1 anti-hypertensive medication LVEF ≥ 50% Current BP < 160/100 mmHg 	
 Known cardiovascular disease or risk factors (other than hypertension) or use of cardiac medications (other than anti-hypertensives or statins) Diabetes Mellitus

HFpEF	
 • Physician confirmed Dx of HF • Symptomatic HF (NYHA II or III) • LVEF \geq 50% • \uparrowLV filling pressures (see text) • Current BP < 160/100 mmHg 	
 • Prior history of LVEF < 50% • Acute decompensated HF • \geq Moderate valvular disease • Significant arrhythmias (AF, SVT, VT) • Pericardial disease • Congenital heart disease • 1' Pulmonary Arterial hypertension
--------------	---	---

HFpEF subjects

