- 2) No known cardiovascular disease, including but not limited to coronary heart disease, heart failure, valvular stenosis or \geq moderate valvular regurgitation, arrhythmias, pericardial disease, stroke, and/or peripheral arterial disease
- 3) No known cardiovascular risk factors, other than hypertension. Specifically, no current or prior history of smoking, obesity, chronic kidney disease, or rheumatologic disorders.
- 4) No known use of cardiovascular medications, other than anti-hypertensives, lipid lowering agents and/or aspirin for primary prevention. Specifically, no current therapy with digoxin and/or anti-arrhythmic medications.

Detailed exclusion criteria for hypertensive controls

- 1) Age < 50 years old
- 2) Inability to provide written informed consent
- 3) Known coronary artery disease (prior myocardial infarction, coronary revascularization, or stenosis >50%), or subjects with symptoms or signs of acute myocardial ischemia, for example unstable angina or cardiovascular instability, who may be at greater risk
- 4) Diabetes mellitus
- 5) Valvular heart disease (\geq moderate stenosis or regurgitation)
- 6) Pericardial disease
- 7) Right ventricular failure and/or pulmonary arterial hypertension.
- 8) Inability to lie flat for non-invasive cardiac imaging procedures
- 9) Estimated glomerular filtration rate < 45 ml/min/1.73m² and/or on dialysis.
- 10) Indwelling metal that is unsafe/incompatible with cardiac magnetic resonance imaging.
- 11) Any history of adverse reactions or contraindications to cardiac imaging, including adverse reactions and/or contraindications to echocardiographic contrast, gadolinium, 11C-Acetate, or 13N-Ammonia.
- 12) Any history of adverse reactions or contraindications to regadenoson.
- 13) Any history of adverse reactions or contraindications to aminophylline (the reversal agent for regadenoson).

- 14) Uncontrolled hypertension ($\geq 160/100$ mmHg) or symptomatic hypotension (systolic blood pressure < 90 mmHg)
- 15) Obesity, with weight or waist circumference greater than the compatible limit of cMRI and/or PET scanners.
- 16) Active pregnancy.
- 17) Prior cardiac transplant.
- 18) Inability to complete cardiac imaging procedures over 2 consecutive days.
- 19) Inability to fast for 6 hours and abstain from caffeine intake for > 24 hours
- 20) Non-English speaking

Healthy Controls

Detailed inclusion criteria for healthy controls

- 1) Age ≥ 50 years old regardless of sex and race

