- 2) No known cardiovascular disease, including but not limited to coronary heart disease, heart failure, valvular stenosis or \geq moderate valvular regurgitation, arrhythmias, pericardial disease, stroke, and/or peripheral arterial disease
- 3) No known cardiovascular risk factors, including but not limited to hypertension, diabetes mellitus, smoking, obesity, chronic kidney disease, or rheumatologic disorders.
- 4) No known use of aspirin, statins, and cardiovascular medications, including but not limited to beta-blockers, inhibitors of the renal-angiotensin-aldosterone axis, diuretics and/or other anti-hypertensive medications, digoxin, and/or anti-arrhythmic medications.

Detailed exclusion criteria for healthy controls

- 1) Age < 50 years old
- 2) Inability to provide written informed consent
- 3) Known coronary artery disease (prior myocardial infarction, coronary revascularization, or stenosis $> 50\%$), or subjects with symptoms or signs of acute myocardial ischemia, for example unstable angina or cardiovascular instability, who may be at greater risk
- 4) Diabetes mellitus
- 5) Valvular heart disease (\geq moderate stenosis or regurgitation)
- 6) Pericardial disease
- 7) Right ventricular failure and/or pulmonary arterial hypertension.
- 8) Inability to lie flat for non-invasive cardiac imaging procedures
- 9) Estimated glomerular filtration rate < 45 ml/min/1.73m² and/or on dialysis.
- 10) Indwelling metal that is unsafe/incompatible with cardiac magnetic resonance imaging.
- 11) Any history of adverse reactions or contraindications to cardiac imaging, including adverse reactions and/or contraindications to echocardiographic contrast, gadolinium, ¹¹C-Acetate, or ¹³N-Ammonia.
- 12) Any history of adverse reactions or contraindications to regadenoson.

- 13) Any history of adverse reactions or contraindications to aminophylline (the reversal agent for regadenoson).
- 14) Obesity, with weight or waist circumference greater than the compatible limit of cMRI and/or PET scanners.
- 15) Active pregnancy.
- 16) Prior cardiac transplant.
- 17) Inability to complete cardiac imaging procedures over 2 consecutive days.
- 18) Inability to fast for 6 hours and abstain from caffeine intake for >24 hours
- 19) Non-English speaking

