- B) Myocardial blood flow reserve by Gd enhanced cMRI (MPRI) is correlated with CFR by ¹³N-Ammonia PET.
- C) Subendocardial MPRI is lower than subepicardial MPRI in HFpEF.
- D) Subendocardial MPRI is progressively impaired from healthy to hypertensive to HFpEF.
- E) Myocardial blood flow reserve is positively correlated with LV diastolic function.
- F) Myocardial blood flow reserve is positively correlated with LV systolic function.

Analysis for aim 1. Primary outcome: Myocardial blood flow reserve, as measured by MPRI from contrast enhanced cMRI first pass perfusion imaging and CFR from ¹³N-Ammonia PET perfusion imaging will be compared between the three study groups: healthy, hypertensives, and HFpEF. The distributions of each within each study group will be assessed using histograms, Q norm plots, and the Shapiro Wilk test. If normally distributed then analysis of variance will be used to test for differences in myocardial blood flow reserve between groups. If the p-value from the ANOVA is < 0.05, then pairwise comparisons using unpaired t-tests with unequal variances will be made between groups using a Bonferroni correction. If MPRI or CFR is not normally distributed, then a Kruskal-Wallis test and Wilcoxon rank sum tests will be used in place of ANOVA and t-tests. The null hypothesis is that myocardial blood flow reserve does not differ among HFpEF patients, healthy individuals, and hypertensive individuals. We will also assess correlations (Spearman) between myocardial blood flow reserve, age, gender, blood pressure, heart rate, and body mass index. To account for potential confounders, multivariable linear regression models will be constructed with myocardial blood flow reserve as the dependent variable, study group as the primary independent variable, with adjustments for age, gender, race/ethnicity, anti-hypertensive medications, systolic blood pressure, heart rate, body mass index, LVEF, LV end diastolic volume, and LV mass. Prior to entry into models, variables will be log transformed, as appropriate. We will check model fit by residual plots. Missing data will not be imputed as we will attempt to replace subjects with significant amounts of missing data due to uninterpretable images, as detailed above.

Statistical power for Aim 1: Using a one-way ANOVA at $p = 0.05$, we present between group differences in myocardial blood flow reserve as assessed by CFR under different sample size and power scenarios in **Table 4**. We anticipate

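### Excluding risk factors from hypertensive controls but not from HFpEF builds confounding into the HFpEF contrasts, and the control definitions need reconciling

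*Combined protocol and SAP*

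**What the plan says.** **Control groups.** For the hypertensive group, Section 2.2.1 states: "Hypertensive subjects with other cardiovascular risk factors (as previously defined) will be excluded to reduce confounding". The earlier definition is in the healthy-cohort paragraph of the same section: "cardiovascular risk factors (hypertension, DM, tobacco use, dyslipidemia, family history of cardiovascular disease, CKD, autoimmune disorder". Table 2 and the detailed lists in Section 2.2.2 also exclude diabetes from both control groups.

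**HFpEF group.** The HFpEF criteria in Sections 2.2.1 and 2.2.2 exclude, among other things, coronary disease, eGFR below 45, pressure of 160/100 or above, and body size beyond scanner limits. They do not exclude diabetes, tobacco use, dyslipidemia, family history, autoimmune disease, or CKD with eGFR of 45 or more.

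**Analysis.** Controls are matched to HFpEF on gender only. The primary tests in Section 3 are an unadjusted ANOVA or Kruskal-Wallis test. The Aim 1 regression is fitted "with adjustments for age, gender, race/ethnicity, anti-hypertensive medications, systolic blood pressure, heart rate, body mass index, LVEF, LV end diastolic volume, and LV mass". Aims 2 and 3 add resting myocardial blood flow.

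**Detailed control lists (Section 2.2.2).** For hypertensive controls: "Specifically, no current or prior history of smoking, obesity, chronic kidney disease, or rheumatologic disorders". Permitted drugs there: "No known use of cardiovascular medications, other than anti-hypertensives, lipid lowering agents and/or aspirin for primary prevention". Table 2 words the drug exception differently: "use of cardiac medications (other than anti-hypertensives or statins". For healthy controls: "No known cardiovascular risk factors, including but not limited to hypertension, diabetes mellitus, smoking, obesity, chronic kidney disease, or rheumatologic disorders".

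**The concern.** A restriction removes confounding from a comparison only if it applies to both sides. Coronary disease is handled that way: Table 2 excludes it from every group. Diabetes, tobacco use and known CKD are removed from the controls alone, so in this sample they become markers of HFpEF.

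The affected contrast is a main one. HFpEF versus hypertension is part of the primary hypothesis of each of Aims 1-3. The Specific Aims text names the difference in oxidative metabolism between hypertensive and HFpEF patients as an open question. The trend analyses across the three groups inherit the same imbalance. A positive result could reflect HFpEF, the comorbidities that come with it, or both, and no planned analysis separates them.

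The second concern is practical. The control definitions differ between places, so two screeners could reach different decisions on the same volunteer.

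**Working it through.** The plan states no figure on this point, so there is none to reproduce. The check compares criteria and then illustrates the size.

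**1. Where the factors stand**

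| Factor in the 2.2.1 list | Barred in hypertensive controls | Barred in HFpEF | Term in the group-comparison models |
|---|---|---|---|
| Hypertension | no (defines the group) | no | indirect (systolic pressure, anti-hypertensive drugs) |
| Diabetes | yes | no | none |
| Tobacco use | yes | no | none |
| Dyslipidemia | yes in 2.2.1, but see step 5 | no | none |
| Family history | yes in 2.2.1; not in the detailed list | no | none |
| CKD | yes, no threshold | only eGFR below 45 or dialysis | none |
| Autoimmune disorder | yes | no | none |

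Six of the seven have no term in any group-comparison model. The eGFR floor of 45 applies to all groups, so the kidney asymmetry lies only in the undefined bar on known CKD. The clearest cases are diabetes and tobacco use.

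**2. Size of the induced difference (illustration for CFR)**

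Difference = (prevalence in HFpEF − prevalence in controls) × effect in SD × SD.

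- From the plan: SD 0.90, and a detectable largest-to-smallest difference of 0.87 with 20 per group (Section 3, power for Aim 1). The 0.87 is taken as printed and serves only as a scale.
- Assumed: 20-60% of HFpEF subjects have any of the three factors, prevalence in controls is 0, and the effect is a 0.3-0.8 SD reduction.
- Low end: 0.2 × 0.3 = 0.06 SD; × 0.90 = 0.05 CFR units, about 6% of 0.87.
- High end: 0.6 × 0.8 = 0.48 SD; × 0.90 = 0.43 CFR units, about 50% of 0.87.
- Intermediate: 0.4 × 0.5 = 0.20 SD = 0.18 CFR units. With only the HFpEF mean shifted, the noncentrality is 20 × 0.20² × 2/3 = 0.533, and the three-group ANOVA at 0.05 rejects 9.0% of the time even if HFpEF itself has no effect.
- With equal prevalence in the groups the difference is 0.

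**3. Why a covariate does not repair it**

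If no control has the factor, its coefficient is estimated from HFpEF subjects alone. With one such factor and no other covariates, the adjusted contrast is simply factor-free HFpEF minus controls. HFpEF subjects with the factor have no comparator. At 40% prevalence, 12 HFpEF subjects carry the contrast: standard error 0.90 × √(1/12 + 1/20) = 0.33, against 0.90 × √(1/20 + 1/20) = 0.28 unadjusted.

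**4. Precision of an explicit restricted comparison**

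Standard error in SD units = √(1/n + 1/20), where n is the number of HFpEF subjects left.

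| HFpEF left | Standard error | Change from 20 |
|---|---|---|
| 20 | 0.316 | – |
| 16 | 0.335 | +6% |
| 12 | 0.365 | +15% |
| 8 | 0.418 | +32% |

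These rows correspond to 20%, 40% and 60% having *any* of the three factors. If the prevalence applied to each factor separately, and independently (assumption), then 20% each leaves 20 × 0.8³ ≈ 10 (+22%), 40% each leaves 20 × 0.6³ ≈ 4 (+68%, using 4.32), and 60% each leaves about 1.

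**5. Control definitions side by side**

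- *Obesity:* absent from the 2.2.1 list; a named risk factor in both detailed control lists; separately excluded in those same lists only above scanner limits. No BMI threshold is given.
- *Dyslipidemia:* barred in hypertensive controls through 2.2.1, while Table 2 allows statins and the detailed list allows lipid-lowering agents.
- *Aspirin:* allowed in hypertensive controls in the detailed list; not named in the Table 2 exception.
- *CKD:* barred in controls with no threshold; the only number is the floor of 45 common to all groups.

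**The case against.** The strongest reply is that comorbidity belongs to HFpEF. The introduction sets out to describe perfusion, energetics and fibrosis, the hypotheses in Section 2.1 are about association, and one cited paper's title has comorbidities driving myocardial dysfunction in HFpEF. On that view the share due to diabetes or smoking is part of the HFpEF difference. This stands as a choice of what to estimate, but the plan does not state that choice. The introduction also aims at underlying mechanisms, and Section 2.2.1 gives confounding control as the reason for the exclusion.

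The rule also does what it says for hypertensive versus healthy, which the gradient question needs. A reader might infer that it creates confounding throughout the study; the documents do not support that. Nor do they support reading the HFpEF group as held to a looser eGFR limit, since the floor is common.

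A reader might also conclude that the missing covariates are the fault and adding them the cure. Step 3 shows otherwise. The models do adjust for age, BMI, systolic pressure and anti-hypertensive drugs, though none of these stands in for diabetes or smoking.

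Finally, prevalence and effect are assumptions, and the low end of the range is negligible. That is correct and limits what can be claimed about size.

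**Conclusion.** The point holds as a cheap improvement. The one-sided exclusion builds confounding by diabetes, tobacco use and, less clearly, CKD into HFpEF versus either control group. The planned analysis neither separates these factors nor labels the contrast accordingly.

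The illustrated contribution is 0.05-0.43 CFR units against 0.87. It rests wholly on the assumed prevalence of any factor (20-60%) and effect (0.3-0.8 SD). The documents supply neither, and they give no basis for a size in Aims 2 and 3. It would be wrong to infer that an observed HFpEF-hypertension difference would be spurious; the documents show only that its source could not be identified.

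The conflicts between the control definitions are plain in the text and depend on no assumption.

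**What to change.** **Section 3, Aims 1-3.** Pre-specify a sensitivity analysis comparing HFpEF subjects free of diabetes, tobacco use and CKD with hypertensive controls, reported as an estimate with a confidence interval. State how each factor is determined from the history, creatinine and chemistry already planned in Section 2.3. Describe the main contrast as HFpEF with its comorbidities versus isolated hypertension.

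**Sections 2.2.1 and 2.2.2, including Table 2.** Reconcile the control definitions on obesity, on dyslipidemia versus permitted statins or lipid-lowering agents, on aspirin, and on the CKD threshold. The choice is the sponsor's. In deciding on obesity, note that excluding it only in controls would limit the overlap on which the planned BMI adjustment depends.

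**Cost.** Some wording in Section 3 and an eligibility clarification, with no new procedures or subjects. The restricted analysis is less precise (6-32% larger standard error with 16 to 8 HFpEF subjects left, and more if the factors are each common), so it may be inconclusive and should be presented as such.
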